## 2.5 STATISTICAL ANALYSIS

### 2.5.1 Sample Size Determination

We plan to enroll 30 subjects with PAH, allowing for a conservative drop-out rate of 10%, in this open label trial of oral CXA-10. We expect to see decrease in the PVR after 12 weeks of therapy. The intention to treat (ITT) population will consist of all subjects who have received at least one dose of study medication. To estimate our effect size for power calculations, we use data from the SUPER-1 sildenafil PAH trial (a randomized placebo control trial evaluating the effects of 20 mg, 40 mg or 80 mg TID of sildenafil in subjects with PH). Using the hemodynamic data from the 80 mg arm of the SUPER-1 trial and making a conservative assumption that our therapy will only have an effect that is 70% of sildenafil (decrease in PVR of 2.3 woods units with SD of 4.1), the sample size required for 80% power and P = 0.05 is 27 subjects (Table 2). We anticipate more than sufficient power to detect vasodilatory effects of NO2-OA administration (decreased PVR) after 3 months of therapy. Based on our extensive phase 1 data with CXA-10 formulations, we

anticipate the drug will cause no systemic blood pressure changes and no increases in methemoglobin levels.

**Table 2 Required sample size for different effect,  
Power =0.8 ,  $\alpha=0.05$ , two sided test**

% of Sildenafil	Mean (SD) PVR change, Woods unit	N
90	3.0 (4.9)	23
80	2.6 (4.2)	23
70	2.3 (4.1)	27

With safety as the primary outcome measure, we use Fleming's single stage phase II design with the following assumptions:  $\alpha = 0.05$ , Power= 0.80, lower proportion for rejection 70% (with no SAEs), higher proportion of acceptance 90% (with no SAEs) with maximum recruited patients of 27 patients resulting in a minimum number of success (with no SAEs to indicate that the treatment is safe) is 24. Thirty patients will be enrolled to compensate for up to 10% lost-to follow-up.

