## **2.4 STUDY ENDPOINTS**

Primary Endpoint:

The primary endpoint measures the incidences of treatment-emergent adverse events.

Secondary Endpoints:

The primary efficacy endpoint measures the change from baseline in Pulmonary Vascular Resistance (PVR) assessed by Right Heart Catheterization at 12 weeks.

Other secondary endpoints measure:

- Change from baseline in hemodynamic parameters including Cardiac Output (CO), Cardiac index (CI), mean Pulmonary Artery Pressure (mPAP), Pulmonary Artery Wedge Pressure (PAWP), Mean Right Atrial Pressure (mRAP), and compliance (SV/ (sPAP-dPAP) at 12 weeks
- Change from baseline in RV function including tricuspid annular plane systolic excursion (TAPSE) and tissue Doppler of the lateral tricuspid valve anulus (S') as assessed by echocardiograms at 12 weeks
- Change from baseline in functional exercise capacity by assessing 6 minute walk distance test with Modified Borg Dyspnea Scale at 12 weeks
- Change from baseline in the levels of serum NT-proBNP at 12 weeks
- Change from baseline in WHO Functional Class at 12 weeks
- Change from baseline in patient reported outcomes measured by PAH-SYMPACT® questionnaire at 12 weeks
- Change from baseline in daily physical activity assessed by personalized activity monitor at 12 weeks
- Pharmacokinetic endpoint: CXA-10 parent and metabolites

Exploratory Endpoints:

- Change in insulin sensitivity by intravenous glucose tolerance test at 12 weeks
- Pharmacodynamic endpoint: change from baseline in serum biomarkers, leptin, inflammatory cytokines (IL-17, IL-6, TNF $\alpha$ , MCP-1) and hsCRP at 12 weeks
- Pharmacokinetic - Pharmacodynamic relationship of CXA-10 on relevant efficacy, safety and biomarkers endpoints, if the data allow
- Epidemiological relationships of oral and gut microbiome and PAH

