## 2.5.2 Statistical Analysis

Change of each outcome from baseline will be presented by median (IQR). Primary analysis will be performed by paired t-test comparing continuous outcome in 12-weeks vs. baseline. All data will be tested for normality, and non-normal data will be tested by Wilcoxon signed rank test. We will also use mixed effect models with restricted maximum likelihood estimation to test the change of outcome during the 12 weeks of intervention.

Demographics and baseline characteristics will be listed and summarized descriptively. Safety will be evaluated via the incidence of AE's, changes in clinical labs, and vital signs. AEs will be coded by system organ class and preferred term according to the most recent edition CTCAE. AEs will be summarized by frequency, severity, and relationship to study medication. Clinical labs will be compared to normal ranges and flagged if found to be of clinical concern. Results will be presented as observed changes and depicting changes from baseline to defined study timepoints.

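### Do the uneven SDs in Table 2 undermine the power stated for the PVR endpoint?

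*Combined protocol and SAP*

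**What the plan says.** Section 2.5.1 bases the PVR calculation on one published trial arm: "Using the hemodynamic data from the 80 mg arm of the SUPER-1 trial". Table 2 scales that arm to three fractions of the sildenafil effect, at 80% power and alpha 0.05 with a "two sided test":

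| Fraction | Mean PVR decrease (WU) | SD (WU) | N |
|---|---|---|---|
| 90% | 3.0 | 4.9 | 23 |
| 80% | 2.6 | 4.2 | 23 |
| 70% | 2.3 | 4.1 | 27 |

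The plan adopts the 70% row: "decrease in PVR of 2.3 woods units with SD of 4.1), the sample size required for 80% power" is put at 27. It enrols 30 to allow for 10% drop-out and then adds: "We anticipate more than sufficient power to detect vasodilatory effects of" the study drug. It gives neither the reference arm's own mean and SD nor the way in which each row's SD was obtained.

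Section 2.5.2 names the test: "Primary analysis will be performed by paired t-test comparing continuous outcome". Section 2.4 places PVR under the secondary endpoints: "The primary efficacy endpoint measures the change from baseline in Pulmonary Vascular Resistance (PVR"). The primary endpoint is treatment-emergent adverse events. Section 2.5.1 gives safety its own Fleming single-stage design, with "maximum recruited patients of 27 patients".

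**The concern.** If one reference arm feeds all three rows, its SD should carry through by one rule. The means do follow one rule, but the SDs do not: they drop by 0.7 between the first two rows and by 0.1 between the next two. As a result, N stays at 23 when the effect falls from 3.0 to 2.6 WU, so the table does not show the usual cost of a smaller effect.

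The row that sets N gives almost exactly 80% power, so a slightly larger SD would take it below target. The sentence about ample power then reads as stronger than the calculation behind it. What would be at stake is the reading of a null PVR result: which decrease could 27 completers have detected?

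**Working it through.** **Inputs.** Means, SDs, alpha, power and sidedness come from Section 2.5.1 and Table 2. The paired t-test comes from Section 2.5.2.

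**Formula.** A paired t-test on n subjects has noncentrality δ = (mean/SD)·√n on n − 1 degrees of freedom. Power is the probability that a noncentral t variable exceeds the two-sided 5% critical value in absolute size.

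**Step 1: reproduce the plan's figures.** For the 70% row, δ = (2.3/4.1)·√27 = 0.561 × 5.196 = 2.915. The critical value on 26 df is 2.056, and power is 80.1%. With 26 subjects it is 78.5%, so 27 is the smallest N that reaches 80%.

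| Row | Mean/SD | Smallest N for 80% | Power at that N |
|---|---|---|---|
| 3.0 (4.9) | 0.612 | 23 | 80.1% |
| 2.6 (4.2) | 0.619 | 23 | 81.0% |
| 2.3 (4.1) | 0.561 | 27 | 80.1% |

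All three printed sample sizes are exact. Enrolment also agrees: 27/(1 − 0.10) = 30.

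**Step 2: look for a rule behind the SDs.** Each printed value is allowed ±0.05 for rounding.

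- *Means.* Dividing by the fraction gives full-arm ranges of 3.278–3.389, 3.188–3.313 and 3.214–3.357. They overlap at 3.278–3.313, so one full-arm mean fits.
- *Constant SD.* 4.9, 4.2 and 4.1 are not equal.
- *Proportional SD.* Dividing by the fraction gives 5.389–5.500, 5.188–5.313 and 5.786–5.929. These do not overlap.
- *Linear in the fraction.* The two steps should be equal. The first lies between 0.6 and 0.8, the second between 0.0 and 0.2.
- *Fixed plus scaled variance* (a + b·f², with a and b not negative). This needs SD₈₀/SD₉₀ of at least 0.8/0.9 = 0.889. The most that rounding allows is 4.25/4.85 = 0.876.

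None of these rules fits. Other rules were not tested, and the reference data are not in the documents.

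**Step 3: what the SD does to power at 2.3 WU.**

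| SD | Where it comes from | Power, n = 27 | Power, n = 30 | Decrease detectable with 80% power, n = 27 |
|---|---|---|---|---|
| 3.68 | 4.2 × 70/80 | 88% | 91% | 2.06 WU |
| 3.81 | 4.9 × 70/90 | 85% | 89% | 2.13 WU |
| 4.1 | 70% row as printed | 80% | 84% | 2.30 WU |
| 4.2 | SD of the 80% row | 78% | 83% | 2.35 WU |
| 4.9 | SD of the 90% row | 65% | 70% | 2.74 WU |

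The largest SD that keeps 80% power is 4.106 with 27 completers and 4.346 if all 30 are analysed.

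**Step 4: the other two rows at the planned size.** With 27 completers, 3.0 (4.9) gives 86.5% and 2.6 (4.2) gives 87.2%. With 30 they give 90.0% and 90.6%.

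**The case for a change.** The strongest case for a change is this. The sponsor holds the reference data and could settle the matter with one line giving the arm's SD and the rule applied to it. Until then, the decrease detectable with 80% power runs from 2.06 to 2.74 WU across the SDs that the table itself suggests. The three extra enrolments are set aside for drop-out, and Section 6.4.8 omits the catheterization for anyone who stops before Week 10, so 30 paired PVR values cannot be assumed.

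Part of this stands. The derivation is not shown, the SDs are irregular, and the remark about ample power is loose for the 70% row.

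The rest carries less weight:

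- **Thin margin.** Any N solved for 80% power has almost no slack at its own inputs. The plan chose the row with the lowest mean/SD ratio, and Section 6.4.8 says that subjects removed from the study are replaced, which helps to protect the 27 completers.
- **The 65% figure.** It joins the effect of the 70% row to the SD of the 90% row, a pairing that the plan never makes. It marks one end of a range and is not an estimate.
- **The remark about power.** If the expected effect is above the deliberately cautious 70%, the other two rows support it, at 86.5% and 87.2%.
- **One fixed SD as the default.** Nothing in the documents favours a fixed SD over a scaled one.

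**Conclusion.** The irregularity in Table 2 is real, but it does not show that any stated figure is wrong. The printed sample sizes are exact for the printed inputs, and the claimed 80% power at 2.3 WU with SD 4.1 is met at 80.1%. Whether the true power is higher or lower cannot be told without the reference-arm SD: the table's own SDs, scaled or carried across rows, put it anywhere from 65% to 88%.

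No change follows. Naming the SD's source and adding a sensitivity range would be good documentation, but N would stay at 27 completers, which the Fleming safety design uses as well. The paired t-test, the endpoint and the planned analyses would also stay the same. Once the trial has run, the confidence interval from the observed changes will show which PVR decreases are compatible with the data, whatever SD was assumed at planning.

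This conclusion assumes that the table's inputs come from the cited arm, as Section 2.5.1 says, and that about 27 subjects have paired PVR measurements.

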	
Potential subjects will undergo a screening visit to determine that eligibility requirements are met. Subjects who meet the inclusion criteria and none of the exclusion criteria will receive oral CXA-10 at the dose of 300 mg once daily for 12 weeks.
 
The first 10 subjects enrolled will receive the first dose of the study drug in the cardiac catheterization laboratory to evaluate acute pharmacological responses during the screening RHC (Visit1). This will be repeated at the end of the 12-week study RHC (Visit 7). Hemodynamic measures such as pulmonary vascular resistance (PVR), mean pulmonary artery pressure (mPAP) and left and right ventricular filling pressures, will be measured at baseline and 30 minutes post drug dose and CXA-10 metabolites will be measured with pharmacokinetics sampling time points at baseline and 2-6 hours post drug. Food will be given prior to dosing. Subjects will have 6-minute walk distance with Borg dyspnea scale assessments. Plasma NT-proBNP level, the World Health Organization (WHO) Functional Class assessment, and a health related quality of life questionnaire will also be collected. To evaluate in vivo insulin action in stimulating glucose disposal, oxidation, and nonoxidative disposal. An intravenous glucose tolerance test (IVGTT) will be performed before and after 12 weeks of CXA-10 treatment.
 
Subjects will be evaluated at 4-week intervals for occurrences of adverse events, laboratory test abnormalities, and evaluations of NT-proBNP plasma levels, six-minute walk distance with Borg dyspnea scale assessments, WHO functional classification and health related quality of life questionnaire recorded. Additional blood samples will be obtained for biomarkers and cytokines analysis, and physical activities will be monitored using a noninvasive accelerometer before and after study drug treatment.

Planned Sample Size:	27 completed subjects
Duration of Treatment:	12 weeks
Major Inclusion Criteria:	
 
• Male or female between 18-80 years of age inclusive at screening
 
• Weight <math>\geq</math> 40 kg or 88 lbs.
 
• Have a WHO Classification of Functional Status Class II or III
 
• Must meet all of the following hemodynamic criteria by means of a right heart catheterization: mPAP of <math>\geq</math>25 mmHg, PVR <math>\geq</math>
 

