### 2.1 CLASSIFICATION AND METHODOLOGICAL DESIGNS

The clinical investigation is a single-center, one-arm, open-label proof of concept safety study and a phase 2a proof of efficacy pre- and post-assessment study of oral CXA-10 for the treatment of PAH. The study aims at assessing the safety and efficacy of 12-week oral CXA-10 therapy on the changes in hemodynamics and exercise capacity in PAH patients. Approximately 30 subjects will be enrolled to ensure at least 27 subjects complete the study.

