### **3. HUMAN SUBJECTS**

The proposed study population will consist of 27 subjects with PAH. In order to achieve this number, it is anticipated that approximately 30 participants may need to be enrolled into this study to account for subjects who may not qualify the eligibility criteria or are withdrawn for any reasons.

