#### **6.4.8. Withdrawal of Subjects and Stopping Criteria:**

##### **STOPPING RULES:**

**Dose Reduction:** If subjects experience an increase of  $\geq 7$  stools/day over baseline or any serious AE believed to be possibly related to the study drug the dose of the study drug may be reduced to 150 mg/day or 75 mg/day at the discretion of the physician investigator. Subjects may be asked to return to the clinic for an unscheduled visit to assess their status if deemed necessary

based on the clinical judgement of the physician investigator. This unscheduled visit may require blood draws, vital signs and/or review of concomitant medication.

**Withdrawal of Subjects:** Subjects must be withdrawn from the study for the following reasons:

- Systolic BP < 80 mmHg
- Liver function test abnormalities: if ALT and/or AST > 8X ULN, the subject should stop taking study drug immediately. Medical evaluation should be undertaken as appropriate to the signs and symptoms manifested by the subject
- Positive pregnancy test

Subjects may be withdrawn from the study for the following reasons:

- At their own request
- At the specific request of the Investigator (eg: detection of a new significant safety concern related to the study drug)
- Occurrence of intercurrent diseases which in investigator's opinion, continuation of the study drug would be harmful to the subject's well-being
- Pertinent non-compliance with the conditions for the trial or instructions by the investigator
- Lost to follow up

Any subject removed from the study will remain under medical supervision until the condition is medically acceptable. Study subjects removed from the study will be replaced by enrolling another volunteer with similar demographics.

Subjects not completing the entire study should be fully evaluated when possible according to the following schedule:

- If study medication is discontinued on or prior to Week 4, complete all protocol required assessments scheduled for the End of Treatment visit excluding the RHC.
- If study medication is discontinued after Week 4 but prior to Week 10, complete all protocol required assessments scheduled for the End of Treatment visit excluding the RHC.
- If study medication is discontinued on or after Week 10 and prior to the start of the End of Treatment visit, complete all protocol required assessments scheduled for the End of Treatment Period.

All withdrawn subjects will be asked to report to the clinic for a follow-up visit (Visit 9).

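### The 24-of-27 safety rule has 72% power, not the stated 80% (exact alpha 2.0%), and no cut-off at 27 patients meets both stated error rates

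*Combined protocol and SAP*

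**What the plan says.** Section 2.5.1 makes safety the primary outcome and describes a Fleming "single stage phase II design with the following assumptions": alpha 0.05 and "Power= 0.80, lower proportion for rejection 70% (with no SAEs), higher proportion of acceptance 90% (with no SAEs"). The resulting rule is "maximum recruited patients of 27 patients resulting in a minimum number of success (with no SAEs to indicate that the treatment is safe) is 24". The section does not say whether alpha is one- or two-sided for this rule, and it does not report the alpha and power that 24 of 27 attains.

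The number of patients is described in several ways:

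- Section 2.5.1: "Thirty patients will be enrolled to compensate for up to 10% lost-to follow-up". The same section defines the ITT population as everyone who received at least one dose.
- Synopsis: "27 completed subjects".
- Section 2.1: "Approximately 30 subjects will be enrolled to ensure at least 27 subjects complete the study".
- Section 3: about 30 enrolled "to account for subjects who may not qualify the eligibility criteria or are withdrawn for any reasons".
- Section 6.4.8: "Study subjects removed from the study will be replaced by enrolling another volunteer with similar demographics".

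None of these gives a safety cut-off for a number other than 27, or says whether the 27 are completers or dosed subjects.

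**The concern.** A single-stage rule on a count can attain only certain alpha and power values, and the pair 24 and 27 fixes both. A normal approximation can suggest that 27 patients suffice when no whole-number cut-off at 27 delivers the design rates.

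This rule is the only numerical criterion in the plan for calling the treatment safe. If its power is below 80%, an acceptably safe drug is more likely to miss the criterion than the plan says. If the number analysed is not 27, the rule is undefined, and keeping 24 with a larger number would loosen it.

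**Working it through.** **Inputs, all from section 2.5.1.** n = 27; cut-off r = 24 SAE-free patients; p0 = 0.70; p1 = 0.90; alpha 0.05; power 0.80. Assumption: alpha is one-sided (upper tail), as is usual for this design.

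**Trying to reproduce the plan's 80%.** The normal-approximation sample size is

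n = [(1.645 × √(0.7 × 0.3) + 0.842 × √(0.9 × 0.1)) / 0.2]² = 25.3, so 26.

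The same approximation at n = 27 gives power

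Φ[(0.2 × √27 − 1.645 × √0.21) / 0.3] = Φ(0.951) = 82.9%.

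That figure belongs to a continuous boundary at 27 × 0.7 + 1.645 × √(27 × 0.7 × 0.3) = 22.8 patients, in effect a cut-off of 23. Rounding 22.8 to 23 and adding 1 gives 24, which may be how the plan arrived at 24; the documents do not say. The stricter integer rule does not keep the 82.9%.

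**Exact calculation.** With X binomial, alpha = P(X ≥ r | n, 0.70) and power = P(X ≥ r | n, 0.90).

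For 24 of 27, summing the terms for 24, 25, 26 and 27:

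- Power: 0.2333 + 0.2520 + 0.1744 + 0.0581 = 0.7179 (to rounding).
- Alpha: 0.0151 + 0.0042 + 0.0008 + 0.0001 = 0.0202.

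Neighbouring cut-offs at n = 27:

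| Cut-off | Alpha | Power |
|---|---|---|
| 23 | 0.0591 | 0.8734 |
| 24 | 0.0202 | 0.7179 |
| 25 | 0.0051 | 0.4846 |

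No row has both alpha at or below 0.05 and power at or above 0.80. The shortfall at 24 is 80.0 − 71.8 = 8.2 percentage points. A two-sided reading (upper tail 0.025) does not change this: 24 still meets the alpha limit and its power is still 71.8%.

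Solving P(X ≥ 24 | 27, p) = 0.80 gives p = 0.914, so the rule reaches 80% power only at a true SAE-free rate of about 91.4%.

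**Other numbers of patients.** Smallest cut-off with alpha at or below 0.05:

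| n | Cut-off | Alpha | Power | Both rates met? |
|---|---|---|---|---|
| 24 | 21 | 0.0424 | 0.7857 | no |
| 25 | 22 | 0.0332 | 0.7636 | no |
| 26 | 23 | 0.0260 | 0.7409 | no |
| 27 | 24 | 0.0202 | 0.7179 | no |
| 28 | 24 | 0.0474 | 0.8579 | yes |
| 29 | 25 | 0.0379 | 0.8416 | yes |
| 30 | 26 | 0.0302 | 0.8245 | yes |
| 31 | 27 | 0.0239 | 0.8068 | yes |
| 32 | 28 | 0.0189 | 0.7885 | no |
| 33 | 28 | 0.0414 | 0.8939 | yes |

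Keeping 24 as the cut-off with more patients gives alpha 0.0932 at n = 29 and 0.1595 at n = 30 (power 0.9742).

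**The case against.** The arithmetic is not in dispute; the case against goes to its weight.

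- **The error is on the safe side.** The chance of wrongly declaring safety is 2.0% against 5% allowed, and 27 patients are separately justified by the PVR calculation in Table 2. This stands for n = 27. It does not give the safety rule its stated power.
- **The true SAE-free rate may exceed 90%.** Section 6.4.5 counts as SAEs only events thought related to the study. Section 1.3.3 reports no SAEs in the oral Phase 1 studies and no treatment-related SAEs so far in the FSGS study. At an assumed 95%, the power of 24 of 27 is about 96%. This is plausible but not shown in PAH patients, and the plan's power is stated at 90%.
- **Safety is otherwise descriptive.** The primary endpoint is the incidence of treatment-emergent AEs (section 2.4), section 2.5.2 plans summaries only, and the rule appears only under sample size. This tempers the severity. Even so, section 2.5.1 presents the count as indicating that the treatment is safe.
- **The number of patients is largely settled.** Enrolment of 30 and replacement both aim at 27. But section 2.1 allows more than 27 completers, more than 27 may be dosed, and the rule names no analysis set. This is a gap in specification, separate from the power error.
- **Cut-offs by number dosed are a redesign with costs.** This is fair; the costs are set out with the fix.

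**Conclusion.** The concern holds. As written, 24 of 27 attains alpha 2.0% and power 71.8%, and no cut-off at 27 meets both stated rates. A drug with a true 90% SAE-free rate would fail the rule 28% of the time instead of the planned 20%. The power figure needs only independent patients and the stated 90%; it does not depend on whether alpha is one- or two-sided.

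There is no inflation of alpha at 27. It appears only if 24 is carried to a larger number: 9.3% at 29 and 16.0% at 30. The point should be fixed, but it does not undermine the trial.

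**What to change.** **Minimum.** Add one sentence to section 2.5.1 stating that 24 of 27 attains alpha 2.0% and power 72% by exact binomial calculation, and say which patients make up the 27. The cost is a less favourable stated power.

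**Alternative, with no added enrolment.** Apply the rule to all subjects who receive at least one dose and fix the cut-off in advance by number dosed:

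- 24 of 28, 25 of 29, 26 of 30 or 27 of 31, all of which meet both rates.
- For 24 to 27 or 32 dosed, where no cut-off meets both, use the smallest cut-off with alpha at or below 5% and report the attained power: 21 of 24 (79%), 22 of 25 (76%), 23 of 26 (74%), 24 of 27 (72%) or 28 of 32 (79%).

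This changes the analysis set for the rule and needs a short table. It also needs a statement of how to count a dosed subject lost before Week 12 with no recorded SAE. One option is observed SAE status up to last contact, including Visit 9, with a sensitivity analysis counting such subjects as failures.

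Both ways of counting have a price. Observed status credits shortened follow-up as success. The sensitivity analysis is severe: with 30 dosed and 3 lost (the planned 10%), 26 of the 27 observed subjects would have to be SAE-free, which has about 23% power at a true 90%. It should therefore be labelled as a sensitivity analysis, not as the decision rule.
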